6. SYNOPSIS

Study Title: A Multicenter, Randomized, Parallel Group, Double Blind, Multiple Dose, Placebo Controlled Study to Assess the Efficacy and Safety of MNK-1411 in Male Subjects 4 to 8 Years of Age With Duchenne Muscular Dystrophy	
Protocol Number: MNK14112096	Type: Phase 2
Condition/Disease:	Duchenne Muscular Dystrophy
Approximate Number of Subjects: 132	Approximate Duration of Subject Participation: 24 weeks for the Blinded Treatment Period, Open Label Extension Period until study termination.
Approximate Number of Study Centers: 50 globally	Approximate Duration of Study: The Blinded Treatment Period portion of the study is estimated to be 3 years.
Design: This is a multicenter, double blind, placebo controlled, multiple dose study to examine the safety and efficacy of MNK-1411 in male subjects 4 to 8 years of age (inclusive) with Duchenne Muscular Dystrophy (DMD). Approximately 150 subjects will be screened in order to randomize 132 (44 per treatment group). Following a screening period of up to 28 days, subjects will be randomized on a 2:2:1:1 basis to receive 24 weeks of treatment with 2 weight based doses of MNK-1411 or volume matched placebo administered 2x/week. Subjects will return to the clinic for visits at 4, 8, 12, 16, and 24 weeks after their first dose of study drug. Subjects who complete the 24-week Blinded Treatment Period will be eligible to enter an Open Label Extension Period where all subjects will receive treatment with MNK-1411. Participation in the Open Label Extension Period will continue until the subject chooses to discontinue treatment, the investigator feels that treatment is no longer indicated, MNK-1411 is approved and marketed, or the sponsor ceases development of this compound for DMD. All subjects will complete a 2-week drug taper after their last full dose of study drug and a follow-up visit 28 (\pm 7) days after their last full dose of study drug. The taper is not required for any subject who has a hypersensitivity reaction to the study drug.	
Objectives: Primary Objective To determine the effect of MNK-1411 on motor function in subjects with DMD. Secondary Objectives To assess the effect of MNK-1411 on motor skills and strength. To determine the safety and tolerability of MNK-1411 in subjects with DMD. Exploratory Objectives 	

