
• Treatment A: MNK-1411 0.5 mg (0.5 mL, for subjects weighing more than 20 kg) or 0.4 mg (0.4 mL, for subjects weighing less than or equal to 20 kg) administered SC 2 times per week (2x/week) (administered on either Sunday and Wednesday, Monday and Thursday, Tuesday and Friday, or Wednesday and Saturday).• Treatment B: MNK-1411 0.25 mg (0.25 mL, for subjects weighing more than 20 kg) or 0.2 mg (0.2 mL, for subjects weighing less than or equal to 20 kg) administered SC 2x/week (administered on either Sunday and Wednesday, Monday and Thursday, Tuesday and Friday, or Wednesday and Saturday).• Treatment C: Volume matched placebo (0.5 mL for subjects weighing more than 20 kg or 0.4 mL for subjects weighing less than or equal to 20 kg) administered SC 2x/week (administered on either Sunday and Wednesday, Monday and Thursday, Tuesday and Friday, or Wednesday and Saturday).• Treatment D: Volume matched placebo (0.25 mL for subjects weighing more than 20 kg or 0.2 mL for subjects weighing less than or equal to 20 kg) administered SC 2x/week (administered on either Sunday and Wednesday, Monday and Thursday, Tuesday and Friday, or Wednesday and Saturday).	
During the Open Label Extension Period, subjects will be treated with MNK-1411 at the dose administered during the Blinded Treatment Period. If a subject requires a switch in dose (eg, switch to low dose due to being unable to tolerate high dose, or switch to high dose based on increased weight [eg, as subject grows with age]), the investigator should consult with the medical monitor. No switches in dose are permitted during the Blinded Treatment Period.	
All subjects will complete a 2-week taper after their last full dose of study drug. In the first week of the taper, each subject will receive one-half of their original dose administered 2x/week for 1 week, followed by one-half of their original dose administered 1 time per week for 1 week. The taper is not required for any subject who has a hypersensitivity reaction to the study drug.	
Efficacy Evaluations:	
The following efficacy assessments will be evaluated: 10 Meter Walk/Run, North Star Ambulatory Assessment (NSAA), Time to Climb 4 Standardized Stairs, Time to Stand from A Supine Position, quantitative muscle testing, pulmonary function tests, and biomarkers.	
Pharmacokinetic and Pharmacodynamic Evaluations:	

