The pharmacokinetics (PK) of MNK-1411 in DMD patients will be characterized using population PK modeling with sparse PK sampling implemented in this study. The exposure response (selected efficacy and/or safety endpoints at Week 4) relationship will be explored.	
Safety Evaluations:	
The following safety assessments will be evaluated: adverse events, medical history, physical examinations, concurrent medical conditions, height, weight, clinical laboratory tests, vital signs, electrocardiograms, and antidrug antibodies.	

Study Title: A Multicenter, Randomized, Parallel Group, Double Blind, Multiple Dose, Placebo Controlled Study to Assess the Efficacy and Safety of MNK-1411 in Male Subjects 4 to 8 Years of Age With Duchenne Muscular Dystrophy

Protocol Number: MNK14112096	Type: Phase 2
Condition/Disease:	Duchenne Muscular Dystrophy

Quality of Life/ Health Outcome Evaluations:

The following quality of life /health outcome assessment will be evaluated: Pediatric Outcomes Data Collection Instrument (PODCI).

Statistical Methods:

Analysis Populations

The following analysis populations are defined for this study:

- The Modified Intent-to-Treat (mITT) Population will include all randomized subjects who receive 1 or more doses of study drug and who contribute any efficacy data to the study.
- The Safety Population will include all subjects who receive 1 or more doses of study drug.
- The PK Population will include all subjects who provide at least 1 quantifiable concentration of ACTH₁₋₂₄ following the administration of at least 1 complete dose of study drug, and without any major protocol deviations that compromise the PK samples.

Sample Size

A total of 132 subjects will be randomized in this study (44 per treatment group). The sample size was determined using the change from baseline in the 10 Meter Walk/Run time. With 37 subjects per treatment group expected to complete the Blinded Treatment Period, the trial will have an 80% power to detect a 1 second treatment difference comparing 2 groups at a significance level of 0.05. Taking into account a dropout rate of approximately 15%, the sample size for this study will be 44 subjects per treatment arm.

Efficacy Analysis

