Unless otherwise specified, all statistical tests will be two-sided with a significance level of 0.05. Summary statistics will be provided for all study variables with descriptive statistics (number of observations, mean, SD, median, minimum, and maximum) for numerical (or continuous) variables, and frequency and percentages will be calculated for categorical variables. All data will be summarized by treatment groups as appropriate. The 2 placebo groups will be combined for all analyses. Data summary and analyses will be performed with SAS 9.4 or higher.

The primary efficacy endpoint is a change from baseline in 10 Meter Walk/Run time at Week 24. The primary statistical analysis method for the endpoint will be performed using an analysis of variance (ANOVA) model with treatment as a main factor and baseline value as a covariate.

The secondary efficacy endpoints will be analyzed using the same statistical method as that for the primary efficacy endpoint.

Additional exploratory analyses [REDACTED]
[REDACTED]

Pharmacokinetic Analysis

Population PK analysis for MNK-1411 will be conducted using nonlinear mixed effects modeling.

Safety Analysis

Treatment-emergent adverse events and serious adverse events will be summarized using the appropriate version of MedDRA by preferred term within system organ class. Other safety data will be listed and summarized descriptively or graphically, as appropriate.

Study Title: A Multicenter, Randomized, Parallel Group, Double Blind, Multiple Dose, Placebo Controlled Study to Assess the Efficacy and Safety of MNK-1411 in Male Subjects 4 to 8 Years of Age With Duchenne Muscular Dystrophy

Protocol Number: MNK14112096	Type: Phase 2
Condition/Disease:	Duchenne Muscular Dystrophy

Quality of Life/Health Outcomes Analysis

The PODCI (sport and physical functioning domain and transfer/basic mobility domain) will be summarized at baseline and each study visit. Change from baseline to Weeks 4, 8, 12, 16, and 24 in PODCI domains also will be summarized. The change from baseline data will be analyzed using the same methods as those used for the primary efficacy endpoint.

Open Label Extension Analysis

In the Open Label Extension Period, efficacy data will be summarized at each visit. Safety data will also be summarized as appropriate.

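### Combining the two placebo volumes for all analyses hides the only comparisons that can separate injection volume from drug for volume-dependent events such as injection-site reactions

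*Combined protocol and SAP*

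**What the plan says.** All references are to the Synopsis (section 6) of the combined protocol and SAP.

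- **Active arms** (Study Drug and Treatment Administration): "Treatment A: MNK-1411 0.5 mg (0.5 mL, for subjects weighing more than 20 kg" and "Treatment B: MNK-1411 0.25 mg (0.25 mL, for subjects weighing more than 20 kg". At or below 20 kg the figures are 0.4 mg in 0.4 mL and 0.2 mg in 0.2 mL.
- **Placebo arms** (same section): "Treatment C: Volume matched placebo (0.5 mL for subjects weighing more than 20 kg" and "Treatment D: Volume matched placebo (0.25 mL for subjects weighing more than 20 kg", with 0.4 mL and 0.2 mL at or below 20 kg. C therefore matches A in volume, and D matches B.
- **Allocation** (Design): "subjects will be randomized on a 2:2:1:1 basis".
- **Sizing** (Sample Size): "A total of 132 subjects will be randomized in this study (44 per treatment group"), so placebo counts as one group there.
- **Pooling** (Efficacy Analysis): "The 2 placebo groups will be combined for all analyses". The neighbouring sentences set summary statistics for every study variable and summaries of all data by treatment group as appropriate.
- **Safety**: safety and tolerability are a secondary objective. Adverse events are summarised by preferred term within system organ class, and other safety data descriptively or graphically. No exception to pooling is given, no safety test is specified, and no separate injection-site assessment is listed, so local reactions would be recorded as adverse events.

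**The concern.** In the active arms, dose and injection volume cannot be told apart: whoever receives twice the dose also receives twice the volume. The placebo arms vary volume alone, so they hold the information needed to separate the two. Once C and D are merged, that information leaves the tables. Both active arms are then set against the same half-and-half mixture of volumes, which matches neither.

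This matters only for events that might depend on the volume injected, chiefly injection-site reactions, in a trial with subcutaneous injections twice a week for 24 weeks. For such events, part of a difference between the dose columns could be read as a drug effect when it is due to volume. Because the safety tables are descriptive, readers will compare columns by eye, with nothing in the table to warn them.

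**Working it through.** **1. The plan's own numbers.** 37 completers per group with about 15% dropout: 37/0.85 = 43.5, rounded up to 44. Then 3 × 44 = 132, and 132 split 2:2:1:1 gives A 44, B 44, C 22, D 22. The stated sizes reproduce, with placebo as one pooled group of 44.

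**2. Volume and dose.** A: 0.5 mg/0.5 mL or 0.4 mg/0.4 mL. B: 0.25 mg/0.25 mL or 0.2 mg/0.2 mL. Every active injection is 1 mg/mL, and within each weight band A has twice the volume of B.

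**3. Effect of pooling.** Let pA, pB, pC and pD be the event rates. The pooled placebo rate is P = (22pC + 22pD)/44 = (pC + pD)/2.

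- (pA − P) − (pA − pC) = pC − P = +(pC − pD)/2
- (pB − P) − (pB − pD) = pD − P = −(pC − pD)/2

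In the difference between the two dose effects, P cancels: (pA − P) − (pB − P) = pA − pB, so a pooled placebo corrects nothing. The matched form, (pA − pC) − (pB − pD) = (pA − pB) − (pC − pD), removes the volume effect, provided that volume adds the same number of points on drug as on placebo.

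**4. Illustration with no drug effect.** The rates are assumed; the documents give none.

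| High / low volume rate | P | A − P | B − P | A − B | A − C and B − D |
|---|---|---|---|---|---|
| 20% / 10% | 15% | +5 | −5 | +10 | 0 |
| 30% / 15% | 22.5% | +7.5 | −7.5 | +15 | 0 |
| 40% / 20% | 30% | +10 | −10 | +20 | 0 |

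In 200,000 simulated trials per row, the observed order B < P < A occurred in about 43%, 55% and 65%. The order P ≤ B < A, which resembles an ordinary dose response, occurred in about 22%, 19% and 15%.

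**5. Illustration with a drug effect that is the same at both doses** (also assumed). Take pC = 20%, pD = 10%, and 5 points added by drug: pA = 25%, pB = 15%, P = 15%. Against pooled placebo, A shows +10 and B shows 0. Against matched placebo, both show +5.

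**6. Precision at a 20% rate** (95% half-width = 1.96 × √[0.2 × 0.8 × (1/n1 + 1/n2)]).

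- 44 versus 44 (pooled): 16.7 points
- 44 versus 22 (A versus C, or B versus D): 20.5 points, a ratio of 1.22
- 22 versus 22 (C versus D): 23.6 points

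**7. Why efficacy should stay pooled.** The SD is not stated in the text available. For 80% power, a 1 second difference, two-sided 0.05 and 37 per group, the normal approximation implies SD = √(37/2)/(1.96 + 0.84) ≈ 1.54 s. With that SD, a matched comparison of 37 versus 18.5 completers would have about 63% power.

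**The case against.** A reader might infer that any volume effect would pass for a drug dose effect. The documents do not support that. With a pure volume effect the expected order is B below pooled placebo below A, so the low dose looks better tolerated than placebo, which is a hint that volume is at work. That hint is not dependable: it appeared in about 43% to 65% of the simulated trials, and it vanishes if the drug itself has some local effect (step 5). What stands is that a volume effect could be mistaken for part of a dose effect.

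A reader might also infer that pooling creates a false gradient between the doses. It does not. A minus B contains no placebo term, and its confounding comes from giving both doses at one concentration. Pooling only leaves out the correction.

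Other points on the plan's side stand in full:

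- Volume matching can serve blinding, and the documents do not say that C and D were meant as separate analytical controls. The sizing treats placebo as one group.
- The documents do not say that local-reaction tables will drive the choice of dose, and nothing in them shows a volume effect at these volumes.
- With 22 subjects per placebo arm, a shift of 5 to 10 points lies well inside the uncertainty of a matched contrast.
- C and D remain separate randomised arms, so nothing is lost from the data. The table could still be produced at reporting, but the sentence as worded does not provide for it.

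**Conclusion.** The point holds as a minor improvement to the safety displays, not as an error in the design or in the efficacy analysis. As worded, the pooling rule reaches adverse-event summaries and hides the randomised contrasts that can separate volume from drug. If placebo reaction rates differ by volume, each dose's contrast with placebo is shifted by half that difference, upward for A and downward for B when the larger volume gives more reactions. If they do not differ, the shift is zero.

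The 5 to 10 point shifts shown rest wholly on assumed rates; only the algebra and the arm sizes come from the documents. The text available is essentially the synopsis, with some exploratory wording redacted, so a fuller safety section may already provide the display.

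**What to change.** Keep pooled placebo for efficacy and general safety. Amend the pooling sentence to read, for example: *The two placebo arms are pooled in every analysis, except that injection-site adverse events are also summarised descriptively by the four randomised arms (A, B, C and D).* Show C and D beside the pooled column, so that A can be read against C and B against D.

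The cost is one sentence and two extra columns in the injection-site table. Sample size, allocation, blinding, data collection and efficacy power do not change. The drawback is sparse columns: at a 20% rate the half-width for a matched contrast is about 20.5 points rather than 16.7. The display should carry no tests and should be labelled descriptive.

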- Additional guidance regarding the administration of motor tests (10 Meter Walk/Run, Time to Climb 4 Standardized Stairs, Time to Stand from a Supine Position, North Starr Ambulatory Assessment [NSAA]) has been provided, along with modification of Exclusion criterion 7 to require that subjects be able to complete the 10 Meter Walk/Run test in 10 seconds or less at the Screening and Baseline Visits.

PROTOCOL AMENDMENT 2

SUMMARY OF CHANGES

Protocol Amendment 2 was developed to address the following considerations:

- In a randomized, double-blind, placebo controlled crossover study in patients ages 5 to 8 with Duchenne muscular dystrophy [Beenakker et al, 2005](#) utilized a 2 month washout period between treatment periods with prednisone and placebo and this washout period appeared to be effective. Subsequently a Medical Advisory Board evaluated the current study design and based on their clinical experience recommended allowing the enrollment of subjects who have not received a therapeutic dose of corticosteroids within 2 months prior to the start of the study.
- Subjects with asthma are excluded from the study. Therefore, the concomitant use of inhaled corticosteroids (whose approved indication is for asthma) should not be permitted.

The following changes were made:

Section 12.2, Exclusion criterion 2 was revised to:

2. Subject has had previous systemic treatment with corticosteroids within 2 months prior to the Screening Visit. Exception: In subjects who were down-titrated to a physiological dose of corticosteroids (ie, 3 mg/m² of prednisone or deflazacort) a maximum of 1 month of no greater than a physiological dose followed by 1 month completely off corticosteroids prior to the Screening Visit will be acceptable for study entry. Transient previous use of corticosteroids will be evaluated on a case-by-case basis by the sponsor or designee. The use of topical or intra-articular corticosteroids is permitted during the study.

Section 13.1, the exception for inhaled corticosteroids was deleted.

PROTOCOL AMENDMENT 1

SUMMARY OF CHANGES

Protocol Amendment 1 was developed to address issues raised by the central institutional review board including adding a study drug taper followed by a cosyntropin stimulation test and clarifying parent and/or legal guardian consent.

Additional minor changes that do not impact study conduct or subject safety were also made.

The major protocol changes are summarized below:

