Entry Criteria: Male subjects 4 to 8 years of age (inclusive) with a diagnosis of DMD confirmed by complete dystrophin deficiency, an identifiable mutation of the DMD gene, or complete dystrophin gene sequencing consistent with DMD, and a clinical profile consistent with DMD. Subjects should have serum potassium within the reference range at screening. Subjects taking approved treatments that target gene mutation (eg, eteplirsen or ataluren) may be enrolled in the study if they have been on a stable dose for 30 days prior to the first dose of study drug, and plan to remain on that dose throughout the study. Subjects will be excluded if they have symptomatic cardiomyopathy; have had any previous systemic treatment with corticosteroids within 2 months prior to the Screening Visit; or treatment with immunosuppressants or mineralocorticoids in the 3 months prior to the Screening Visit. Subjects must be able to complete the 10 Meter Walk/Run test in 10 seconds or less at the Screening and Baseline Visits.	

Study Title: A Multicenter, Randomized, Parallel Group, Double Blind, Multiple Dose, Placebo Controlled Study to Assess the Efficacy and Safety of MNK-1411 in Male Subjects 4 to 8 Years of Age With Duchenne Muscular Dystrophy	
Protocol Number: MNK14112096	Type: Phase 2
Condition/Disease:	Duchenne Muscular Dystrophy
Concomitant Medications and Treatments: Subjects are not permitted to receive live or live-attenuated vaccines (with the exception of the varicella zoster vaccine, if needed per Inclusion criterion 6), systemic corticosteroids (eg, prednisone or deflazacort) for DMD, mineralocorticoids, or immunosuppressants during the study. All medications and nondrug therapies (eg, physical therapy, blood transfusions, oxygen supplementation, etc) taken from 30 days prior to the Screening Visit and throughout the study will be recorded.	
Study Drug and Treatment Administration:	
The following treatments will be administered during the 24 week Blinded Treatment Period:	

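### Does the primary analysis need a stated rule for a boy who is assessed at Week 24 but cannot do the 10 Meter Walk/Run?

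*Combined protocol and SAP*

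**What the plan says.** All of this is in Section 6 (Synopsis).

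- **Endpoint and model (Efficacy Analysis).** "The primary efficacy endpoint is a change from baseline in 10 Meter Walk/Run time at Week 24". The model is "an analysis of variance (ANOVA) model with treatment as a main factor and baseline value as a covariate". On the placebo arms: "The 2 placebo groups will be combined for all analyses". Descriptive tables will include the "number of observations, mean, SD, median, minimum, and maximum".
- **Population (Analysis Populations).** The mITT population takes in "all randomized subjects who receive 1 or more doses of study drug and who contribute any efficacy data to the study". A boy who has earlier efficacy data but cannot do the Week 24 test therefore stays in it.
- **Sample size.** The target is 37 completers per group, for 80% power to detect 1 second. Then: "Taking into account a dropout rate of approximately 15%, the sample size for this study will be 44 subjects per treatment arm".
- **Entry (Entry Criteria).** "Subjects must be able to complete the 10 Meter Walk/Run test in 10 seconds or less at the Screening and Baseline Visits". No such requirement is stated for later visits.

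The cover page marks the text as a summary adjusted for disclosure. The amendment summaries point to Sections 12.2, 13.1 and 32.1, which are not included. The Amendment 3 summary also says that more guidance on running the motor tests, the walk/run among them, was added. That guidance is not included either.

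**The concern.** The primary model needs a number of seconds for every boy it uses, and a boy who tries and fails has none. The population definition keeps him, the model as written cannot use him, and nothing in view says what happens next. He has not dropped out, so the 15% allowance does not obviously cover him. The count of observations in the summary tables would show a lost value, but not whether the boy was unable or simply not tested.

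Inability is itself a poor result. Leaving such boys out favours whichever group has more of them. If that is placebo, a real benefit shrinks; if it is an active group, a benefit can appear where there is none. A choice made after unblinding would also be open to challenge.

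**Working it through.** **1. The plan's own figure.** Inputs from Sample Size: 37 completers per group, 15% dropout, three groups after the placebo arms are combined.

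- 37 / (1 - 0.15) = 43.5, rounded up to 44 per group.
- 44 x 3 = 132, as stated.
- Check: 44 x 0.85 = 37.4.

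**2. Implied SD.** None is given in the text available. With difference 1 s, two-sided 0.05, 80% power and n = 37:

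SD = 1 / [(1.960 + 0.842) x sqrt(2/37)] = 1 / (2.802 x 0.2325) = 1.535 s (normal approximation).

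The t test gives 1.515 s, used below.

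**3. Loss of numbers alone.** If one, two or three boys per group have no value for reasons unrelated to their result, a t test with 36, 35 or 34 per group has 78.9%, 77.7% or 76.5% power. The effect is small.

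**4. Selective loss.** Simulation, all inputs assumed unless given above:

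- three groups of 37, with change SD 1.515 s;
- baseline mean 6.5 s and SD 1.5 s, limited to 3-10 s; Week 24 time not below 2.5 s;
- mean change 0 s on both active groups and +1 s on placebo;
- analysis of change on treatment and baseline, high dose against placebo.

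Each range runs between two definitions of the unable boys: exactly the slowest at Week 24 (tight), or chosen by slowness plus equal random noise (loose).

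| Unable boys | Left out | Worst Week 24 time seen | Ranks, unable worst | Velocity, unable = 0 |
|---|---|---|---|---|
| None | 80% | 80% | 78% | 66% |
| 1 on placebo only | 74-75% (estimate 0.92-0.94 s) | 80-82% | 78-79% | 72-73% |
| 3 on placebo only | 62-67% (estimate 0.80-0.86 s) | 82-88% | 80-83% | 83-84% |
| 1 in each group | 80-81% | 74-78% | 75-76% | 57-58% |
| 2 in each group | 79-81% | 68-77% | 71-74% | 49-51% |

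Percentages are power. With three unable on placebo only, the estimate falls short of 1 s by 1 - 0.86 = 0.14 to 1 - 0.80 = 0.20 s.

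With no true effect and three unable in each active group, all left out, the false benefit is 0.13-0.19 s. Active is then wrongly declared better in roughly 6-9% of trials, against a nominal 2.5%.

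**5. How realistic are these boys?**

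- Loose definition, one unable per group: their underlying Week 24 times have a median of 9.9 s, and about half are at or under 10 s, quick enough to meet the entry limit.
- Tight definition, one unable per group: the median is 11.1 s.

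So the simulation mostly labels ordinary walkers as unable. Boys who had truly lost the ability would be slower, so each would count for more, but there would probably be fewer of them. The table shows direction and rough scale. It is not a forecast.

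**6. How many?** One to three of 37 is 3-8% per group. No figure in the documents supports any of these counts.

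**The case for a change.** The best case for acting is that the request is cheap and the timing matters. A sentence and a reason code cost almost nothing, and whether a boy was unable or not tested may be hard to reconstruct later. Balance between groups cannot be assumed in advance, and the bias from leaving boys out can run either way. If the rule already exists, a cross-reference would settle it.

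Much of that stands. The synopsis is silent, the direction of the bias is right, and the figures above can be reproduced.

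It does not show a defect in the plan, for three reasons.

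- Silence in a trimmed synopsis says little about the full protocol, the analysis plan, the motor-test guidance or the case report form, and a synopsis would not normally carry this detail.
- Leaving the boys out would be acceptable if stated, so the request is to write something down. It does not ask for a different analysis.
- With one unable boy per group, the results under omission, worst time seen and ranks lie between 74% and 81% power. A long fixed time for unable boys would cost far more, but nothing in the documents proposes one.

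**Conclusion.** No change is needed. The available text does not say how a boy who is assessed but unable at Week 24 enters the primary model. That is missing detail of the kind analysts settle sensibly before unblinding, and it may already be settled in text we have not seen. No stated figure is wrong: 44 per group and 132 in total reproduce.

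If inability is balanced, leaving the boys out keeps power at 79-81% with one or two per group. If it is unbalanced, the estimate shifts by about 0.13-0.20 s towards the group with more unable boys. That takes three such boys in one group, or in each active group, which is an assumption the documents do not support and the 10-second entry limit makes less likely.

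No alternative is better throughout. Ranks and the worst time seen do better when inability falls on placebo only and worse when it is balanced. Velocity scored zero costs about 14 points even with nobody unable (66% against 80%). They are optional supportive analyses, a fair trade-off and not a correction.

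The conclusion rests on the implied SD of 1.515 s and the assumed baseline distribution, and covers the 10 Meter Walk/Run only. It would need another look if inability at Week 24 proved common and clearly uneven between groups.

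### Does the Synopsis need a named primary contrast and a multiplicity rule for the two MNK-1411 doses against pooled placebo?

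*Combined protocol and SAP*

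**What the plan says.** All references are to Section 6, Synopsis, of the combined protocol and SAP.

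- **Objective:** "To determine the effect of MNK-1411 on motor function in subjects with DMD".
- **Design:** 2:2:1:1 randomization to "2 weight based doses of MNK-1411 or volume matched placebo administered 2x/week".
- **Grouping (Efficacy Analysis):** "The 2 placebo groups will be combined for all analyses". This leaves three groups of 44.
- **Primary model (Efficacy Analysis):** an "analysis of variance (ANOVA) model with treatment as a main factor and baseline value as a covariate", applied to change in 10 Meter Walk/Run time at Week 24.
- **Test level (Efficacy Analysis):** "all statistical tests will be two-sided with a significance level of 0.05". A proviso at the start of that sentence leaves room for a different rule elsewhere.
- **Sample Size:** with 37 completers per group, "the trial will have an 80% power to detect a 1 second treatment difference comparing 2 groups at a significance level of 0.05". The two groups are not identified.
- **Secondary endpoints:** "The secondary efficacy endpoints will be analyzed using the same statistical method as that for the primary efficacy endpoint".
- **PODCI:** "The change from baseline data will be analyzed using the same methods as those used for the primary efficacy endpoint".

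The Synopsis states no order of doses, no adjustment and no gate between tests. The redaction in Efficacy Analysis follows the mention of exploratory analyses, so it does not hide part of the primary analysis sentence.

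**The concern.** A three-level treatment factor yields several candidate tests: the overall F-test, each dose against placebo, the two doses combined against placebo, or a dose trend. The primary objective asks one question about MNK-1411, and the Synopsis does not say which test answers it. On the Synopsis alone, the choice could be made after the data are seen.

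The Sample Size paragraph speaks of two groups at the full 0.05. That can be read as two separate dose-versus-placebo tests with no adjustment, which gives the drug two chances to succeed. If the F-test was meant instead, the stated 80% power describes a different test. The same model carries over to the secondary endpoints and PODCI, and so does the silence.

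**Working it through.** **Inputs from the Synopsis.** 132 randomized at 2:2:1:1; 37 completers per group; dropout about 15%; difference 1 s; two-sided 0.05; power 80%. No SD is given. The error rates below do not need one; the power figures do.

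**1. The plan's own figure.** 37 / (1 − 0.15) = 43.5, rounded up to 44 per group; 3 × 44 = 132. This matches. The allocation is 44:44:22:22, or 44:44:44 after pooling placebo.

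**2. Correlation of the two dose comparisons.** With equal groups of size n, each difference has variance 2σ²/n, and the shared placebo mean gives covariance σ²/n. The correlation is (σ²/n) / (2σ²/n) = 0.5.

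**3. Each dose tested at two-sided 0.05, neither dose effective.**
- In the drug's favour: 1 − Φ₂(1.96, 1.96; 0.5) = 0.0454. One test gives 0.025. Two independent tests would give 1 − 0.975² = 0.0494.
- Either direction: 0.0907, against 0.05.
- With t statistics on 3 × 37 − 4 = 107 degrees of freedom, simulation gives 0.0452 and 0.0905.

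**4. The same null under other readings.**

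| Reading of the primary test | False positive, any direction | In the drug's favour |
|---|---|---|
| Each dose at 0.05, either win counts | 9.0–9.1% | 4.5% |
| Overall F-test alone | 5.0% | not directional |
| Dose comparisons only after a significant F | 4.2% | 2.1% |
| One pre-named dose, combined doses, or trend | 5% | 2.5% |
| Fixed sequence of the two doses | about 5% | about 2.5% |

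Only the first row is inflated. The F-gated route also holds when one dose works and the other does not: with three groups, simulation gives 4.9–5.0% for the ineffective dose.

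**5. Cost of adjusting (assumed SD).** Back-solving from the stated 80% by the normal formula gives SD = 1 / [√(2/37) × (1.960 + 0.842)] = 1.54 s. The t version gives 1.51 s.
- Bonferroni, per dose at SD 1.54 s: Φ(2.802 − 2.241) = 71%.
- Dunnett-type limit, per dose at SD 1.54 s: Φ(2.802 − 2.212) = 72%.
- Holm, per dose, simulated at SD about 1.51 s: about 77% if both doses give 1 s, about 72% if the other dose has no effect.
- F-gated comparison, per dose, simulated at SD about 1.51 s: about 76% if both doses give 1 s or only one works; about 70% if they give 1 s and 0.5 s.
- Fixed sequence: 80% for the first-tested dose; the second depends on the first.

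**6. Does the stated 80% mislead if the F-test is meant?** Over SD 1.51–1.54 s, F-test power is 82–84% if both doses give 1 s or only one does. It is 70–71% if they give 1 s and 0.5 s. The stated figure is close in the first two patterns and optimistic in the third.

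**The case for a change.** The strongest case for a change is this. The trial is randomized, double blind and placebo controlled, with a named primary endpoint and a formal power claim, and a primary analysis should identify its primary test in any phase. The gap is not caused by redaction. Under the dose-by-dose reading, error in the drug's favour nearly doubles. The remedy would be one paragraph with no extra subjects, and if the full protocol already holds a rule, aligning the Synopsis takes one line.

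Much of this stands: the Synopsis is silent on the contrast, and the arithmetic is right under its condition. Three things limit its force.

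- **Only the summary is visible.** The public file is marked as adjusted for disclosure and holds the amendment summaries, abbreviations and Synopsis. It points to Sections 12.2, 13.1 and 32.1, none of which is included. A contrast and testing order would normally sit in the full statistical section. Silence in a synopsis does not show silence in the plan.
- **No promise is broken.** The Synopsis sets a level per test and nowhere claims an overall 5% rate. It labels the trial Phase 2 and makes no confirmatory claim in the supplied text. The secondary and PODCI analyses likewise carry no claim of controlled error.
- **The remedy is a menu.** Fixed sequence, Holm, Dunnett and F-gating each protect something different and each cost something different. None is so clearly better for a two-dose Phase 2 trial that its absence is an error.

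**Conclusion.** No change follows. What remains is narrow: the Synopsis does not name the primary contrast or say how the two doses are handled. An analyst can fill that gap sensibly from the stated model, for example by comparing each dose with placebo only after a significant F-test. That stays within 5% with three groups and needs no departure from the design.

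The size at stake is about 4.5% against 2.5% for a false finding in the drug's favour. It arises only if both doses are tested at the full 0.05 with no gate, either win counts as success, and neither dose has any effect. It assumes equal groups sharing one placebo arm. The other readings considered show no such inflation. Moving to Bonferroni or a Dunnett-type limit would lower per-dose power from 80% to about 71–72% at the back-solved SD, which is a fair trade-off for a Phase 2 sponsor to weigh.

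The conclusion would differ if the full statistical section claimed overall 5% control, or a confirmatory result, while testing both doses unadjusted. Nothing in the supplied text says so.
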